3.2. Secondary Endpoint(s)

3.2.1. Key Secondary Efficacy Endpoints

The key secondary efficacy endpoints are:

- Response based on ≥ 4 points improvement from baseline in the Peak Pruritus Numerical Rating Scale (NRS) from baseline at Weeks 2, 4, and 12.
- Change from baseline in Pruritus and Symptoms Assessment for Atopic Dermatitis (PSAAD) total score at Week 12.

Detailed descriptions of how the Peak Pruritus NRS and PSAAD are derived are provided in Appendix 6 and Appendix 7, respectively.

3.2.2. Secondary Efficacy Endpoints

- Response based on at least 4 points improvement in the Peak Pruritus NRS from baseline at all scheduled time points other than Weeks 2, 4 and 12.
- Time to achieve at least 4 points improvement in the Peak Pruritus NRS from baseline.
- Response based on the EASI-75 at all scheduled time points except Week 12.
- Response based on the IGA of clear (0) or almost clear (1) and 2 point reduction from baseline at all scheduled time points except Week 12.
- Response based on a $\geq 50\%$, $\geq 90\%$ and 100% improvement in the EASI total score (EASI-50, EASI-90 and EASI-100) at all scheduled time points.
- Change from baseline and Percent Change from Baseline in the percentage Body Surface Area (BSA) affected at all scheduled time points.
- Response based on BSA $< 5\%$ at Week 12.
- Percent Change from Baseline in EASI at all scheduled time points.
- Response based on a $\geq 50\%$ and $\geq 75\%$ improvement in Scoring Atopic Dermatitis (SCORAD50, SCORAD75) from baseline at all scheduled time points.
- Change from baseline and Percent Change from Baseline at all scheduled time points in Scoring Atopic Dermatitis (SCORAD) total score and subjective assessments sleep loss.
- Percent Change from Baseline in Peak Pruritus numerical rating scale (PP-NRS) from Days 2-15, Weeks 4, 8 and 12.
- Week 12 Corticosteroid-free days.
- Detailed descriptions of how the BSA and SCORAD are derived are provided in Appendix 5 and Appendix 8 respectively.

3.3. Other Endpoint(s)

3.3.1. Patient-Reported Outcomes

- Change from baseline at Week 12 in Children's Dermatology Life Quality Index (CDLQI) and at all other scheduled time points.
- Change from baseline at Week 12 in Hospital Anxiety and Depression Scale (HADS) and at all other scheduled time points.

- Change from baseline at Week 12 in Patient Oriented Eczema Measure (POEM) and at all other scheduled time points.
- Change from baseline at Week 12 in Dermatitis Family Impact (DFI) questionnaire.
- Change from baseline of Patient Global Assessment (PtGA) at Week 12 and at all other scheduled time points.
- Change from baseline of EuroQol Quality of Life 5 Dimension Youth Scale (EQ-5D-Y) at Week 12 and at all other scheduled time points.
- Change from baseline of Pediatric Functional Assessment of Chronic Illness Therapy Fatigue Scale (Peds FACIT-F) at Week 12 and at all other scheduled time points.
- Response based on Achieving ≥ 2.5 -point Improvement from Baseline in the CDLQI Score at all scheduled time points;
- Response based on the PtGA of clear (0) or almost clear (1) (on a 5 point scale) and a reduction from baseline of ≥ 2 points at all scheduled time points.

Detailed descriptions of how the Patient-Reported Outcomes are derived are in the B7451036 Protocol Appendixes 17, 19, 18, 25, 15, 16 and 21, respectively.

3.3.2. Immunogenicity Sub-study Endpoint

- Fold increase from pre-vaccination baseline at 4 weeks post-vaccination in concentrations of IgG against:
 - Tetanus toxoid;
 - Diphtheria toxoid;
 - Pertussis toxoid (PT);
 - Pertactin (PRN);
 - Filamentous hemagglutinin (FHA);
 - Fimbriae types 2 and 3 (FIM).

The fold increase is defined as the ratio (post-vaccination: pre-vaccination) of concentration values. The natural logarithm of the ratio values will be used for analysis purposes. Each concentrations of IgG will be analyzed individually.

CCI [REDACTED]

[REDACTED]

I

3.4. Baseline Variables

In general, baseline will be defined as defined based on observations collected on or prior to the day of first dose. Baseline values for demographics, medical history, tobacco and alcohol history, AD disease history and prior AD treatments will be based on measures collected at Visit 1/Screening visit. Study Day 1 is defined as the day the subject receives first dose of study drug. If a value is missing on Day 1, then the last available observation before Day 1 will be used. For the PSAAD score, baseline will be defined as the average of all values recorded from Day -6 until Visit 2 / Day 1. Baseline disease severity will be defined by the IGA score (moderate [IGA = 3] vs. severe [IGA = 4] AD) on Visit 2/Day 1. For analysis purposes, randomization strata information will be taken from the Case Report Form (CRF).

3.5. Safety Endpoints

Safety will be assessed by the spontaneous reporting of AEs, physical examinations, and clinical laboratory results in all subjects who receive at least one dose of the investigational product. Unscheduled safety assessments may be performed at any time during the study to assess any perceived safety concerns. Endpoints will be assessed as:

- Incidence of treatment emergent adverse events;
- Incidence of SAEs;
- Incidence of AEs leading to discontinuation;
- The incidence of clinical abnormalities and change from baseline in clinical laboratory values, ECG measurements, and vital signs.

The safety endpoints will be defined in accordance with Clinical Data Interchange Standards Consortium (CDISC) aligned CaPS (CaPS).

3.5.1. Adverse Events

An adverse event will be considered a Treatment-Emergent Adverse Event (TEAE) if the event started during the effective duration of treatment. All events that start on or after the first dosing day and time/start time, if collected, but before the last dose plus the lag time (28 days) will be flagged as TEAEs. The algorithm will not consider any events that started prior to the first dose date.

A 3-tier approach will be used to summarize AEs. Under this approach, AEs are classified into 1 of 3 tiers. Different analyses will be performed for different tiers (see Section 6.6.1).

Tier-1 events: These are prespecified events of clinical importance and are maintained in a list in the product's Safety Review Plan.

090177e19618b8f5\Approved\Approved On: 25-Jan-2021 08:47 (GMT)

Tier-2 events: These are events that are not tier 1 but are “common”. A Medical Dictionary for Regulatory Activities (MedDRA) preferred term (PT) is defined as a Tier-2 event if there are at least 4 in any treatment group.

Tier-3 events: These are events that are neither Tier-1 nor Tier-2 events.

3.5.2. Laboratory Data

Below is a list of hematology and serum chemistry test parameters.

- Hematology: hemoglobin, hematocrit, red blood cell count and indices, reticulocyte count, platelet count, white blood cell count with differential, total neutrophils, eosinophils, monocytes, basophils, lymphocytes, lymphocyte subsets (markers), coagulation panel.
- Serum chemistry: blood urea nitrogen, creatinine, creatine phosphokinase, glucose (non-fasting), sodium, potassium, chloride, calcium, total bicarbonate, aspartate aminotransferase (AST), alanine aminotransferase (ALT), gamma-glutamyl transferase (GGT), bilirubin, alkaline phosphatase, lactate dehydrogenase, uric acid, albumin, total protein, total cholesterol, low-density lipoprotein (LDL), high-density lipoprotein (HDL), triglycerides.

Detailed descriptions of the laboratory data and other tests are in the B7451036 Protocol Appendix 2.

3.5.3. Vital Signs, including Height and Weight

Vital sign measurements are pulse rate and blood pressures.

Height and weight are collected at pre- and post-treatment.

3.5.4. Physical Examinations

Complete physical examinations consist of assessments of general appearance; skin; head, eyes, ears, nose and throat; mouth, heart; lungs; breast (optional); abdomen; external genitalia (optional); extremities; neurologic function; and lymph nodes.

4. ANALYSIS SETS (POPULATIONS FOR ANALYSIS)

Data for all participants will be assessed to determine if participants meet the criteria for inclusion in each analysis population prior to unblinding and releasing the database and classifications will be documented per standard operating procedures.

Population	Description
Full Analysis Set (FAS)	
All participants randomly assigned to study intervention and who take at least 1 dose of study intervention. Participants will be analysed according to the intervention they are randomized to. Analyses for binary endpoints that are defined based on a threshold of change from baseline (eg, NRS4) will also require the baseline value to be equal to or greater than that threshold (eg, for NRS4, the baseline value needs to be ≥ 4). For continuous endpoint change from baseline and percent change from baseline, subjects must have baseline value to be included in the analysis.

Per-Protocol Analysis Set (PPAS)	
The Per Protocol Analysis Set (PPAS) is defined as a subset of FAS who had no major protocol violations. The subjects excluded from the PPAS will be determined and documented before the study is unblinded. This set will include subjects who:
 
 • Met inclusion criteria 1: be 12 to <18 years of age, inclusive, at the time of signing the informed consent. • Had valid and non-missing baseline efficacy data (IGA, EASI). • Met inclusion criteria 2 of documented prior qualifying treatment for AD. • Did not permanently discontinue assigned study oral treatment prior to Week 12. • Had actual, observed IGA and EASI scores at Week 12. • Did not take a protocol-prohibited therapy for the primary diagnosis (high potency TCS or systemic medication or phototherapy). • Did not take a protocol prohibited (CYP2C19/CYP2C9 inhibitor and/or inducer drugs) concomitant medication. • Have an overall compliance of $\geq 80\%$ but $\leq 120\%$ with randomized oral treatment at Week 12. • Adhered to standardized background topical therapy guidelines for $\geq 80\%$ of treatment days and had used at least one medicated background topical therapy during treatment period.

090177e19618b8f5\Approved\Approved On: 25-Jan-2021 08:47 (GMT)

Population	Description
	
 Had no other major protocol violations that is likely to affect materially the clinical observations, or the responses of the patient determined by the clinical team.
Safety Analysis Set (SAF)	All participants randomly assigned to study intervention and who take at least 1 dose of study intervention. Participants will be analysed according to the intervention they actually received.
Immunogenicity Sub-study Analysis Set	All eligible participants participating in the sub-study. The sub-study participants will remain in their treatment groups as previously randomized in the main study.

FAS is the analysis set for all the estimands defined in Section 2.1.

5. GENERAL METHODOLOGY AND CONVENTIONS

5.1. Hypotheses and Decision Rules

PF-04965842 200 mg QD will be declared superior to placebo if the null hypothesis of no difference between PF-04965842 200 mg QD versus placebo for **both** co-primary endpoints is rejected at the 5% significance level. Similarly, PF-04965842 100 mg QD will be declared superior to placebo if the null hypothesis of no difference between PF-04965842 100 mg QD versus placebo for **both** co-primary endpoints is rejected at the significance level specified below.

[figure not shown]
The familywise Type-I error rate for assessing the co-primary and key secondary endpoints will be strongly controlled at 5% (2-sided) using a sequential, Bonferroni-based iterative multiple testing procedure.

The procedure will first assess the co-primary endpoints (IGA and EASI-75 at Week 12 for 200 mg QD vs placebo) at the 5% level. If this hypothesis is not rejected, then all subsequent hypotheses will not be considered statistically significant. If this hypothesis is rejected, then assessing for statistical significance will continue as follows:

- The hypothesis for severity of pruritus (Peak Pruritus NRS4) 200 mg QD vs placebo at Week 2 will be assessed at the 2.5% level. If this hypothesis is rejected, then the unused alpha level of 2.5% will be passed on to the assessment for the key secondary endpoints and the co-primary endpoints for 100 mg QD vs placebo, in the order specified in Sequence A at a 5% significance level (see figure below). All subsequent hypotheses from any point where a hypothesis cannot be rejected will not be considered statistically significant.

- If the hypothesis for severity of pruritus (Peak Pruritus NRS4) 200 mg QD vs placebo at Week 2) is not rejected at the 2.5% level, then the hypotheses for the key secondary endpoints and the co-primary endpoints for 100 mg QD vs placebo, in the order specified in Sequence A will be assessed at a 2.5% significance level (see figure below). If all hypotheses in this sequence are rejected, then the unused alpha level of 2.5% will be passed on to the assessment of the hypothesis for severity of pruritus (200 mg QD vs placebo) at Week 2 at the 5% level. All subsequent hypotheses from any point where a hypothesis cannot be rejected will not be considered statistically significant.

Figure 2. Schematic for Multiple Testing Procedure

The figure above (Figure 2) illustrates the procedure showing the sequence of the tests. Hypotheses for all other endpoints not described here are to be tested at the nominal 5% (2-sided) significant level, without adjusting for multiple comparisons.

5.2. General Methods

In general, for descriptive analyses, number and percent will be presented for binary variables. Number, mean, standard deviation, median, first and third quartiles will be presented for continuous variables.

090177e19618b8f5\Approved\Approved On: 25-Jan-2021 08:47 (GMT)

Estimates of the pairwise differences along with its two-sided 95% confidence interval will be provided among the active treatment groups, PF-04965842 200 mg QD, PF-04965842 100 mg QD and placebo.

5.2.1. Analyses for Binary Endpoints

Binary data at each scheduled visit will generally be analyzed by two approaches: (1) the test of hypothesis (and the p-value) of no difference between two treatment groups will be conducted by the Cochran-Mantel-Haenszel (CMH) statistic adjusting for baseline disease severity (IGA = 3 or IGA = 4); p-values from the CMH statistic will be used to test the hypothesis of no difference in binary responses between two treatment groups; and (2) the proportion of responders in each treatment group will be reported and differences between two treatment groups will be summarized by the weighted difference and its 95% confidence interval obtained by normal approximation. The difference in proportions will be calculated within each randomization stratum. The final estimate of the difference in proportions will be a weighted average of these stratum-specific estimates using CMH weights. The CMH weight w_k for stratum k ($k = 1, 2$) is given by,

$$w_k = \frac{\frac{n_{ik} n_{ck}}{n_{ik} + n_{ck}}}{\sum_{j=1}^2 \frac{n_{ij} n_{cj}}{n_{ij} + n_{cj}}}$$

where n refers to sample size, the subscript c refers to a comparator group (eg, placebo) and the subscript i refers to a test group (eg, an active treatment group). The difference is estimated as $\hat{d} = \sum_{k=1}^2 w_k (\hat{p}_{ik} - \hat{p}_{ck})$, where \hat{p} refers to the estimated proportion.

Two-sided 95% confidence intervals for the difference (based on a normal approximation) are formed by:

$$\hat{d} \pm 1.96 \sqrt{\sum_{k=1}^2 w_k^2 \left(\frac{\hat{p}_{ik}(1 - \hat{p}_{ik})}{n_{ik}} + \frac{\hat{p}_{ck}(1 - \hat{p}_{ck})}{n_{ck}} \right)}$$

In the above formula, the standard error is $\sqrt{\sum_{k=1}^2 w_k^2 \left(\frac{\hat{p}_{ik}(1 - \hat{p}_{ik})}{n_{ik}} + \frac{\hat{p}_{ck}(1 - \hat{p}_{ck})}{n_{ck}} \right)}$. When the number of responders is zero ($x = 0$), then \hat{p} will be replaced by $0.5/(n + 1)$.

The 95% confidence interval for the response rate in each treatment group will also be provided using Wald normal approximation (or the Clopper-Pearson exact method when there are no or all responders in one group).

For the Immunogenicity Sub study, the Clopper-Pearson exact method will be used to compute the associated 95% confidence interval for each treatment, while unconditional exact method proposed by Chan and Zhang will be used to compute the difference in proportions.

090177e19618b8f5\Approved\Approved On: 25-Jan-2021 08:47 (GMT)

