A total sample of 225 participants, with 75 participants randomized to PF-04965842 200 mg QD, 75 participants randomized to PF-04965842 100 mg QD, 75 participants randomized to matching placebo (1:1:1 randomization) is planned. This would provide at least 80% power to detect a difference of at least 20% in IGA response rate between either dose of PF-04965842 and placebo, assuming the placebo response rate is 12% at Week 12. This will also provide at least 96% power to detect a difference of at least 30% in EASI-75 response rate between either dose of PF-04965842 and placebo, assuming the placebo response rate is 23% at Week 12.

For a given dose (PF-04965842 200 mg QD or 100 mg QD), both co-primary endpoints must achieve statistical significance to meet the primary objective.

The familywise Type I error rate (for testing the co-primary and key secondary endpoints) will be strongly controlled at 5% (2-sided) using a closed-testing method based on a sequential, iterative Bonferroni type approach as outlined in Section 5.1.

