6.4. Subset Analyses

Summary statistics for co-primary endpoints will be presented by subgroups below.

- Age (years) group (less than or equal to the median value in FAS, above the median value);
- Sex (Male, Female);
- Race (White, Black or African-American, Asian, Other¹);
- Region of enrollment (US/Canada/Australia, Latin America, Europe, Asia);
- AD Duration (years) group (less than or equal to the median value in FAS, above the median value);

¹ For purposes of analysis, other will comprise the categories of American Indian or Alaska Native, Native Hawaiian or Other Pacific Islander, Multi-Racial and any other category reported on the CRF.

- Baseline disease severity (moderate, severe);
- Baseline EASI group (16-25, >25);
- Baseline % BSA group (10-30, >30-50, >50);
- Previous use of systemic immunosuppressant for AD (Yes, No).

Estimates of the difference between the active dose groups and placebo, along with the 95% confidence interval (no p-value) will be presented for each defined category of each subgroup. For the binary endpoints, analyses will be performed using normal approximation without any adjustments for baseline disease severity.

The primary purpose of the subgroup analyses is to check for consistency of results across subgroups, to make sure overall results are not being driven by some subset of participants.

Graphical display (eg, forest plots) of the differences between treatment groups will be presented, along with the Total difference. There is no intention to have any specific inference within subgroups.

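### SAP 5.2.1 does not confine the zero-responder replacement to the standard error, does not say at what level zero is judged, and has no matching rule for the difference when all respond

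*SAP*

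**What the plan says.** SAP 5.2.1 estimates the treatment difference as a CMH-weighted average of stratum differences over the two baseline severity strata, with a normal-approximation 95% interval. It restates the standard error formula, and the next sentence is the replacement rule: "When the number of responders is zero", the estimated proportion becomes 0.5/(n+1). The same symbol stands in the difference and in the standard error.

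For the interval around a single group's rate, the section switches to Clopper-Pearson when none or all respond. For the difference it covers only the none case.

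P-values for binary endpoints come from the CMH test, separately from this estimate and interval. Three other places depend on the same estimation approach:
- SAP 6.2.3.1 applies it to daily PP-NRS4 from Day 2, to early IGA response and to EASI-100.
- SAP 5.3.1 and Appendix 3 take the estimates and standard errors for the tipping-point analysis from 5.2.1.
- SAP 6.4 says that for binary endpoints in subgroups "analyses will be performed using normal approximation without any adjustments for baseline disease severity", without saying whether the zero rule carries over.

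**The concern.** A small-cell correction is normally there to stop the variance estimate collapsing to zero. If it also enters the point estimate, an empty cell is reported as though a fraction of a patient had responded. Two programmers could follow this text and report different differences from the same data. On the literal reading, an interval can also disagree with the CMH test reported beside it.

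The missing all-responder rule leaves the opposite boundary open. A cell at 100% contributes no variance, so the interval for the difference is somewhat too narrow. What is at stake is the accuracy of reported differences and intervals, chiefly for rare or early endpoints and for the subgroup forest plots, which are meant to show consistency. Trial success is not at stake.

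**Working it through.** **Inputs from the SAP.** 75 per arm ("A total sample of 225 participants, with 75 participants randomized to PF-04965842 200 mg QD"). IGA: "at least 80% power to detect a difference of at least 20% in IGA response rate", "assuming the placebo response rate is 12% at Week 12". EASI-75: "at least 96% power to detect a difference of at least 30% in EASI-75 response rate", "assuming the placebo response rate is 23% at Week 12". Familywise error "will be strongly controlled at 5% (2-sided) using a closed-testing method".

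**Plan's own figures.** With 75 per arm at two-sided 5%, 12% versus 32% gives 84.8% power by normal approximation and 80.7% by Fisher's exact test. 23% versus 53% gives 97.3% and 96.1%. The stated powers are reproduced.

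**Assumption.** The documents give no stratum sizes. I use 45 and 30 per arm.

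**Formulas.** Difference = Σ w_k(p_ik − p_ck). Variance = Σ w_k²[p_ik(1−p_ik)/n_ik + p_ck(1−p_ck)/n_ck]. With equal arms of 45 and 30 the weights are 0.6 and 0.4.

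**1. Shift per empty cell if the rule enters the estimate:** w_k × 0.5/(n_k+1).
- Stratum of 30: 0.4 × 0.5/31 = 0.65 points.
- Stratum of 45: 0.6 × 0.5/46 = 0.65 points.
- Both placebo cells empty: 1.3 points.

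**2. IGA at the planning rates.** Take active 14/45 and 10/30 (32% overall) and placebo 9/45 and 0/30 (12% overall).
- Literal rule: 19.35 (6.6 to 32.2).
- Replacement in the standard error only: 20.0 (7.2 to 32.8).
- Chance of an empty placebo cell at 12%: 0.88^30 = 2.2%; 0.88^45 = 0.3%. If the severe stratum's true placebo rate were 5%, which is not a figure in the documents, it would be 0.95^30 = 21%.

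**3. A rare endpoint.** Active 3/45 and 2/30; placebo 0/45 and 0/30.
- Replaced placebo proportions: 0.5/46 = 0.01087 and 0.5/31 = 0.01613.
- Literal difference: 0.6(0.06667 − 0.01087) + 0.4(0.06667 − 0.01613) = 5.37 points.
- Variance: 0.000584 + 0.000416 = 0.001000, so the standard error is 3.16 points and the half-width 6.20.
- Literal interval: −0.83 to 11.57. Standard-error-only: 6.67 (0.47 to 12.87).
- CMH: observed 5, expected 1.5 + 1.0 = 2.5, variance 0.733 + 0.492 = 1.225. Chi-square = 2.5²/1.225 = 5.10, p = 0.024.

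The literal interval includes zero beside a p-value of 0.024. The standard-error-only interval agrees with the test.

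**4. Direction.** Active 10/45 and 0/30 versus placebo 4/45 and 2/30: the difference moves from 5.33 to 5.98, away from zero. With 0/2 versus 0/6, 0.5/3 − 0.5/7 reports 9.5 points where nobody responded.

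**5. Small subgroups (sizes hypothetical).**
- 1/5 versus 0/5: 0.200 − 0.5/6 = 11.7 points instead of 20.
- Chance of an empty placebo group at 12%: 0.88^10 = 28%; 0.88^5 = 53%.

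**6. All respond.**
- 5/5 versus 5/5: the interval is 0 to 0. With (5.5/6) in the standard error it is ±1.96 × √(2 × 0.0764/5) = ±34.3 points.
- Zero width needs every cell of both arms at 100%. At the EASI-75 planning rates the chance is (0.53 × 0.23)^n for n per arm: 12% at n = 1, 1.5% at n = 2, 0.003% at n = 5, and about 3 × 10⁻⁶⁹ for the full trial.
- All respond on active, 10/45 and 7/30 on placebo: width 18.95 points; with the mirror rule, about 19.6.

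**7. Alternative interval.** For subgroups of 3 to 15 per arm at the planning rates, Miettinen-Nurminen coverage was 94 to 99%, against 89 to 96% for the normal approximation with the replacement in the standard error.

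**The case against.** The strongest reply is that the rule directly follows the standard error formula, so a careful statistician would apply it only there. That reading is plausible, and under it the estimate never moves. But the text does not say so, and the shared symbol allows the other reading. The all-responder gap remains under either.

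The reply is also right on scale. A 0.65-point shift is small against a 20-point planned difference and a half-width of about 12.8 points. An entire placebo arm without IGA responders has a chance of 0.88^75, about 0.007%, so the 5/75 example speaks to rare secondary endpoints, which lie outside the multiplicity procedure. SAP 6.4 limits the subgroup work to the co-primary endpoints, pools smaller race categories, gives no p-values and disclaims inference within subgroups. Miettinen-Nurminen is named in SAP 5.2.6 for Tier-2 adverse events, not efficacy, so using it here is a recommendation rather than a consistency requirement.

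A reader might infer three stronger things that the documents do not support:
- That the rule always shrinks effects. Step 4 shows that it can do the opposite.
- That main-analysis intervals may collapse to zero width. That needs 100% response in every cell of both arms.
- That a mismatch with the crude rates proves an error. A CMH-weighted difference need not equal the crude difference even with no empty cell.

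**Conclusion.** The point holds as a minor defect of specification. The replacement is not confined to the standard error, the level at which zero is judged is undefined, and the interval for the difference lacks an all-responder rule that the single-group interval in the same section has.

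If the rule is read into the estimate, the effect on the IGA co-primary is about 0.65 points per empty cell, and such a cell is unlikely at the planning rate. The effect is material only for rare or early endpoints and for very small subgroups. These sizes rest on assumed strata and hypothetical subgroup sizes. The per-cell shift hardly depends on the split, but the chance of an empty cell does.

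A reader might go further and suppose that the co-primary or key secondary conclusions are at risk. They are not. The binary endpoints in the hierarchy are decided by CMH p-values, and PSAAD is analysed by MMRM. The supplementary tipping-point p-values use the 5.2.1 estimates and standard errors, so they could change slightly.

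**What to change.** In SAP 5.2.1, state that:
- zero is judged per stratum-by-arm cell;
- the 0.5/(n+1) replacement is used only inside the standard error, never in the difference or the reported rates;
- when all respond in a cell, (n+0.5)/(n+1) is used in the standard error in the same way.

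In SAP 6.4, replace the normal approximation for subgroup differences by the Miettinen-Nurminen interval already named in SAP 5.2.6. This also settles whether the zero rule carries over to subgroups.

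The cost is two or three sentences and a small programming change, best made before unblinding. No sample size, test or decision rule is affected.

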9.2. Sample Size Determination

A total sample of 225 participants, with 75 participants randomized to PF-04965842 200 mg QD, 75 participants randomized to PF-04965842 100 mg QD, 75 participants randomized to matching placebo (1:1:1 randomization) is planned. This would provide at least 80% power to detect a difference of at least 20% in IGA response rate between either dose of PF-04965842 and placebo, assuming the placebo response rate is 12% at Week 12. This will also provide at least 96% power to detect a difference of at least 30% in EASI-75 response

rate between either dose of PF-04965842 and placebo, assuming the placebo response rate is 23% at Week 12.

For a given dose (PF-04965842 200 mg QD or 100 mg QD), both co-primary endpoints must achieve statistical significance to meet the primary objective.

The Type-I error rate is set at 5% (two-sided). The familywise Type-I error rate (for testing the co-primary and key secondary endpoints) will be strongly controlled at 5% using a closed-testing method based on a sequential, iterative Bonferroni-type approach as outlined below.

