2.2. Study Design

This is a randomized, double blind, placebo controlled, parallel group, Phase 3 study to evaluate the efficacy and safety of PF-04965842 in adolescent participants 12 to <18 years of age with moderate-to-severe AD co administered with background topical therapy. A total of approximately 225 participants will be enrolled from approximately 100 sites located globally. Participants will be randomized in a 1:1:1 ratio to receive 200 mg PF-04965842 (N=75) or 100 mg PF-04965842 QD (N=75) or matching placebo (N=75) from Day 1. Randomization will be stratified by baseline disease severity (moderate [IGA = 3] vs. severe [IGA = 4] AD). The treatment period is 12 weeks.

In a sub-study, up to approximately 90 participants (up to 30 in each respective study group) who have completed 8 weeks of treatment with study intervention will receive a tetanus, diphtheria and pertussis combination vaccine (Tdap) at Week 8, and will have blood samples collected for the evaluation of immunogenicity to the vaccine at Weeks 8 and 12. The participants in the immunogenicity sub-study will complete all other protocol-specified procedures in the main study. A study design schematic is presented in Figure 1.

Qualified participants completing 12-week treatment with study intervention will have the option to enter the long-term extension (LTE) study B7451015. Participants discontinuing early from the study will undergo a 4 week follow up.

Figure 1. Study Design

Intervention Groups and Duration:

Eligible participants will be randomized into 3 intervention groups in the main study:

Group 1 (N=75): 200 mg PF-04965842 once daily (QD) for 12 weeks (Sub-study: N=up to 30, Tdap vaccination at Week 8).

Group 2 (N=75): 100 mg PF-04965842 QD for 12 weeks (Sub-study: N=up to 30, Tdap vaccination at Week 8).

Group 3 (N=75): placebo QD for 12 weeks (Sub-study: N=up to 30, Tdap vaccination at Week 8).

090177e19618b8f5\Approved\Approved On: 25-Jan-2021 08:47 (GMT)

Sample Size Determination

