6. ANALYSES AND SUMMARIES

6.1. Primary Endpoint(s)

6.1.1. Week 12 IGA Response

6.1.1.1. Main Analysis

- Estimand strategy: Composite, Estimand 1(Section 2.1.1).
- Analysis set: FAS (Section 4).
- Analysis methodology: CMH and normal approximation in Section 5.2.1.
- Intercurrent events and missing data: The intercurrent event is captured through the variable definition; for participants who drop out for any reason, the response will be defined as “non-responsive” after that point.
- The number of participants, number and percent of response at Week 12 along with the 95% confidence interval by normal approximation will be presented for each treatment arm.
- The CMH test p-value, the estimate of the difference in proportions of response at Week 12 along with the corresponding 95% confidence interval by CMH normal approximation will be presented for each PF-04965842 dose group versus placebo.

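### Per-arm 95% intervals for response rates (SAP 5.2.1) use Wald except at 0 or all responders: coverage is somewhat short at rates of 5-15%, and limits are impossible or out of order at 1-3 responders

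*SAP*

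**What the plan says.** SAP 5.2.1 sets out the analysis of binary endpoints in three parts.

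- **Test.** The section says "p-values from the CMH statistic will be used to test the hypothesis of no difference in binary responses between two treatment groups", stratified by baseline disease severity.
- **Treatment difference.** This is a stratum-weighted difference with its own normal-approximation interval.
- **Each arm's response rate.** "The 95% confidence interval for the response rate in each treatment group will also be provided using Wald normal approximation", with one exception: "or the Clopper-Pearson exact method when there are no or all responders in one group".

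The third part carries through to the reporting. For Week 12 IGA response, SAP 6.1.1.1 lists the count and percentage "along with the 95% confidence interval by normal approximation will be presented for each treatment arm". SAP 6.1.2.1 (EASI-75), 6.2.1 (Peak Pruritus NRS4), 6.2.3.1 (other binary efficacy endpoints) and 6.2.4.3 (binary patient-reported outcomes) do the same.

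For the immunogenicity sub-study, SAP 5.2.1 and Protocol Appendix 11 specify Clopper-Pearson for every arm, whatever the count.

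On size, SAP 2.2 says "75 participants randomized to matching placebo (1:1:1 randomization) is planned". The active arms are the same size. The assumed Week 12 placebo rates are 12% for IGA response and 23% for EASI-75.

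**The concern.** The Wald interval is centred on the observed proportion and takes its width from that same proportion. When few participants respond, the estimated standard error is too small and the interval sits too low. A nominal 95% interval then covers less than 95%, and its lower limit can fall below zero. The Clopper-Pearson exception handles the boundary itself, but not the counts next to it, where the approximation is also poor.

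What is at stake is how the per-arm rates read in the published tables, mainly on placebo: intervals somewhat too narrow, limits that cannot be true, and a change of method between 0 and 1 responders. No hypothesis test is at stake.

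**Working it through.** **Inputs.** n = 75 per arm; planned placebo rates 12% (IGA) and 23% (EASI-75); planned differences 20 and 30 points, so active rates of 32% and 53% (SAP 2.2, Protocol 9.2). The Phase 2b placebo IGA rate of 6.3% (Protocol 2.2.2) serves only as a range check.

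**The plan's own figures.** The documents give no coverage figure. Their power figures do reproduce: exact Fisher power at 75 per arm, two-sided 5%, is 80.7% for 32% vs 12% and 96.1% for 53% vs 23%, against the stated 80% and 96%.

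**Step 1: limits at small counts.** Wald: x/75 ± 1.96·√[p̂(1−p̂)/75]. For x = 1: p̂ = 0.0133, half-width = 1.96·√(0.0133·0.9867/75) = 0.0260, giving −1.3% to 3.9%.

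| Responders of 75 | SAP rule | Wilson | Clopper-Pearson |
|---|---|---|---|
| 0 | 0 to 4.8% (exact) | 0 to 4.9% | 0 to 4.8% |
| 1 | −1.3% to 3.9% | 0.2% to 7.2% | 0.03% to 7.2% |
| 2 | −1.0% to 6.3% | 0.7% to 9.2% | 0.3% to 9.3% |
| 3 | −0.4% to 8.4% | 1.4% to 11.1% | 0.8% to 11.2% |
| 9 (12%) | 4.6% to 19.4% | 6.4% to 21.3% | 5.6% to 21.6% |

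The lower limit is negative only for 1, 2 or 3 responders. The upper limit for 1/75 (3.9%) is below that for 0/75 (4.8%), which is out of order.

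**Step 2: coverage at the planned rates.** Coverage at true rate p is the sum of the binomial(75, p) probabilities of all counts whose interval contains p. At p = 12% those counts are 5 to 15: the upper limit for 4/75 is 10.4%, and the lower limit for 16/75 is 0.2133 − 0.0927 = 12.06%. The interval lies wholly below 12% with probability 4.5% and wholly above it with probability 1.5%, so coverage is 100 − 4.5 − 1.5 = 94.0%. At p = 23% the two misses are 5.2% and 1.5%, so coverage is 93.3%. Wilson gives 95.2% and 94.6%; Clopper-Pearson throughout gives 96.9% and 97.3%.

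**Step 3: coverage over ranges.** Exact coverage jumps with n and p, so averages and minima say more than single points. For n = 75 under the SAP rule:

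| True rate | Average | Minimum |
|---|---|---|
| 1-3% | 99.9% | 99.5% |
| 2-5% | 95.4% | 84.6% |
| 5-7% | 90.7% | 85.3% |
| 7-10% | 91.9% | 87.7% |
| 10-15% | 92.8% | 89.2% |
| 15-30% | 93.9% | |
| 30-60% | 94.4% | |

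Varying n from 68 to 82 gives an average of 92.4% at 12% (90.3% to 95.1%) and 93.8% at 23% (91.9% to 95.3%). Wilson averages 95.1-95.4% in each of the three bands between 5% and 15%, with a minimum of 92.9%.

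**Step 4: how often a negative limit arises.** The probability of 1 to 3 responders of 75 is 1.6% at 12%, effectively nil at 23%, and 29% if the placebo rate were 6.3% as in Phase 2b.

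**Step 5: the treatment difference.** The unstratified Wald interval for the difference covers 94.7% at 32% vs 12% and 94.6% at 53% vs 23%. That is close to nominal and gives no reason to change the planned, stratified version.

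**The case against.** The strongest reply is that nothing rests on these intervals. The p-values come from CMH, the treatment effect has its own interval, and the per-arm interval is an additional display. That is correct, and it caps the importance of the point.

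The second reply is that the shortfall is small where the plan expects to be: 94.0% at 12% and 93.3% at 23%. At exactly 6.3% the rule covers 94.7%, the same as Wilson, and at the planned active IGA rate of 32% Wald (95.2%) beats Wilson (93.8%). These figures are right. Single points can flatter or penalise either method, though, and the average shortfall of 2 to 4 points for rates of 5-15% remains.

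A reader might infer three stronger things that do not hold.

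- *The co-primary results would claim materially more certainty than they have.* The shortfall at the planned placebo rates is 1.0 and 1.7 points, in a descriptive interval.
- *The rule undercovers at all low rates.* With the exact method at zero, it covers more than 99% for true rates of 1-3%. Undercoverage and negative limits therefore largely belong to different ranges of the true rate.
- *Placebo rates for EASI-90, EASI-100, SCORAD75 or early visits will be below 12%.* The documents give no rates for these. EASI-90 and EASI-100 cannot exceed EASI-75, planned at 23%, but that alone does not put them below 12%. It is a plausible assumption and should be labelled as one.

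**Conclusion.** The point holds as a minor reporting matter. Under the rule in SAP 5.2.1 with 75 per arm, per-arm intervals average about 91-93% coverage for true rates of 5-15% (minima 85-89%) and about 94% for 15-60%, and they miss mostly by lying too low. With 1 to 3 responders the limits are visibly wrong: negative below, too short above, and out of order relative to 0 responders. At the planned 12% such counts have a 1.6% chance, so this defect matters only if rarer outcomes are tabulated, and whether any are that rare is an assumption.

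The figures assume 75 analysed per arm and simple binomial sampling within an arm. The CMH tests, difference intervals, multiplicity procedure and power do not depend on the per-arm intervals and stand as planned.

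**What to change.** In SAP 5.2.1 specify one per-arm interval method for all counts, with no switch at 0 or all responders, and change the per-arm normal-approximation wording in SAP 6.1.1.1, 6.1.2.1, 6.2.1, 6.2.3.1 and 6.2.4.3 to match. Either of two choices works:

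- **Wilson score interval.** Average coverage is about 95% and no limit falls below zero. Its cost is that coverage can dip at some rates below 3%: the minimum is 89.5% for rates of 0.5-2% and 91.6% for 1-3%.
- **Clopper-Pearson throughout.** Coverage is never below 95%, and it matches the sub-study. Its cost is slightly wider intervals: for 9/75 the width is about 16 points, against about 15 for Wilson or Wald.

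Either is a software option. Sample size, endpoints, tests and the difference intervals stay as they are. Protocol 9.4.2.1 describes an interval only for the difference, so its text need not change.
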